Cost effectiveness is an important issue and while combination of IVIG and rituximab has been advocated, the cost of such treatment is substantial and whether it poses any benefit over rituximab alone, or with other more conventional immunosuppressive agents, has not been established. Both treatment approaches have been previously published in high impact journals.^{3,5} In this study, we aim to evaluate the efficacy and safety of early use of rituximab with or without IVIG in patients with moderate to severe pemphigus using protocols that were similar to those previously published. Apart from complete remission and adverse effects, we will also aim to measure the impact of health care economics and in doing so, assess the cost and benefits of both treatment arms.

Hypothesis:

IVIg in combination with Rituximab is more superior than Rituximab alone in the treatment of moderate to severe pemphigus.

Methods:

Prospective multi-centre, randomised open-label trial

Patients will be randomised to two treatment arms: Rituximab alone or Rituximab + IVIG

Aim to recruit ~10 patients per arm (20 patients in total)

Patients will be reviewed monthly for the first 6 months then 3 monthly in clinic thereafter, follow up will be up to 4 years.

When patient enrolment is confirmed and written consent is obtained, the investigator will open the envelop sequentially and patient will receive the treatment plan stated on the allocation slip. Patient will be randomised to either rituximab arm or rituximab and IVIG arm. The random allocation sequence will be generated using computer-generated random numbers. Randomisation will be to the two arms of the trial in 1:1 ratio. The allocation sequence will be printed on paper slip. A non-study related research assistant will put the slips in to sequentially numbered, opaque, sealed envelopes.

Arm 1 (Rituximab alone arm):

- Rituximab infusion 375mg/m² body surface area (BSA) weekly for 4 weeks from baseline
- Rituximab infusion 375mg/m² BSA weekly for 4 weeks at week 24
- Rituximab infusion 375mg/m² BSA weekly for 4 weeks at week 52
- A total of 12 doses of rituximab will be given in 55 weeks
- If a patient relapses after initial rituximab infusion, further rituximab infusion 375mg/m² BSA weekly for 4 weeks can be given at time of relapse/or if patient fails to achieve complete remission 2 months from last dose of rituximab.

Week 0, 1, 2, 3	Rituximab (375mg/m ²)
Week 24, 25, 26, 27	Rituximab (375mg/m ²)

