Week 52, 53	Rituximab (375mg/m ²)
Week 76, 77	Rituximab (375mg/m ²)

Arm 2: (Rituximab and IVIG arm):⁵

- Rituximab (375 mg/m² BSA) once a week for 4 weeks (week 1, 2, 3) and
- Week 4: Rituximab + IVIG 2g per kg
- Week 5, 6, 7: Above treatment repeated for 2nd cycle, infusion of rituximab (375 mg/m² BSA) once a week for 4 weeks (week 5, 6, 7) and
- Week 8: Rituximab + IVIG 2g/kg
- In week 12, 16, 20, 24 patients received a single infusion of rituximab (375 mg/m² BSA) plus infusion of 2g/kg IVIG
- Thus in 24 week period patients received a total of 12 infusions of rituximab and 7 infusions of IVIG
- If a patient was clinically free of disease at end of 24 weeks, additional infusions of IVIG will be given at week 30, 38, 48, 60 and 76
- A total of 12 doses of rituximab will be given and 12 cycles of IVIG will be given
- If a patient relapses or flares during the treatment, four infusions of rituximab at 375mg/m² BSA will be given at 1-weekly interval will be administered and IVIG 2g/kg will be given at week 4 of treatment after week 32

Week 0	IVIG 2g/kg, divided total dose given over 2-5 days
Week 1, 2, 3	Rituximab (375mg/m ²)
Week 4	Rituximab (375mg/m ²) + IVIG
Week 5, 6, 7,	Rituximab (375mg/m ²)
Week 8	Rituximab (375mg/m ²) + IVIG
Week 12	Rituximab (375mg/m ²) + IVIG
Week 16	Rituximab (375mg/m ²) + IVIG
Week 20	Rituximab (375mg/m ²) + IVIG
Week 24	Rituximab (375mg/m ²) + IVIG
Week 30	IVIG
Week 38	IVIG
Week 48	IVIG
Week 60	IVIG
Week 76	IVIG

For both study arms:

- After initial induction phase for both arms, the time between subsequent doses of rituximab for treatment of relapse should be at least 2 months apart.
- Patients will be followed up for 4 years starting from baseline visit

IVIG and Rituximab

Ahmed et al.⁵⁻⁷ has published data and protocol combining rituximab and IVIG. The theory behind this is that IVIG:

- Contains antibodies directed against B-cell-activating factor belonging to tumour necrosis factor family
- Exact mechanism by which Rituximab and IVIG are effective in induction of prolonged sustained clinical, serological and immuno-pathological remission in patients is not clearly understood – After destroying autoantibody-producing pathogenic B cells, the repopulating B cells do not produce autoantibodies. It is conceivable that in a microenvironment that more closely resembles normal physiology and homeostasis, IVIG could initiate the process of immune restoration.

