- Signs of active infection on CXR
- Positive interferon gamma release assay Quantiferon or T.Spot TB test: must be treated with at least 4 weeks post initiation of isoniazid or other TB therapy
- Inherited or acquired severe immunodeficiency
- History of malignancy
- Patient with active severe infection (excluding fungal infections of the nail), which has required antibiotic treatment within 2 week prior to study enrolment
- Infection requiring hospitalisation or intravenous antibiotic treatment within the last 8 weeks prior to enrolment

- Past history of osteomyelitis, or fasciitis, septic arthritis within the last one year
- Patients with drug induced pemphigus. A thorough medication history will be taken to rule out drug induced pemphigus including D-penicillamine, angiotensin-converting enzyme inhibitors, angiotensin receptor blockers and cephalosporins
- Evidence of any new or uncontrolled concomitant disease that in the investigators' judgement would preclude the patients participation
- Patients with history of allergy or adverse events to IVIG or rituximab treatment¹⁰
- Treatment with intravenous immunoglobulins, plasmaphoresis within the last 8 weeks prior to randomization
- Previous treatment with rituximab or any monoclonal antibody inducing profound lymphopenia
- Treatment with live or attenuated vaccine within the last 28 days prior to randomization

Admission and follow up:

- All infusions will be performed as in-patient procedure of prospective hospital and all patients are to be follow up monthly at out-patient of the prospective Queen Mary Hospital dermatology out-patient clinic
- Patients will be followed up monthly for the first 6 months, then followed up for every 3 months up to 4 years starting from baseline visit

Outcome measures:

Patients' serum will also be taken for desmoglein antibodies and levels will be charted and independent samples t-test will be used to compare the collected data between the two groups. Homogeneity of the treatment groups at baseline will be analyzed using the Mann–Whitney U test and Wilcoxon signed-rank test for independent and dependent variables. The Kaplan-Meier method will be used to estimate the likelihood of reaching the endpoint of relapses or flares within the drug infusing period based on the intention-to-treat population, defined as all patients who has received at least one dose of study medication. The log-rank test will be used to compare time-to-event curves between treatment groups.

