Statistical analysis of results will be done with IBM SPSS statistic program version 25. All tests of significance are two-tailed, and a P value of < 0.05 is considered to indicate statistical significance.

Primary outcome:

- 1) Percentage of participants who achieve relapse-free complete remission

Secondary Outcomes:

- 2) Time to protocol defined disease flare
- 3) Duration of complete remission, evaluated by the PDAI activity score [Baseline up to end of study]
- 4) Number of protocol defined disease flares
- 5) Time to initial complete remission, evaluated by the PDAI activity score [Baseline up to end of study]
- 6) Change in health-related quality of life as measured by the Dermatology Life Quality Index (DLQI) Score [Time Frame: Baseline, Week 4, 12, 24, 36, 48, 60, 72, 84, 96, 120, 144, 168, 192]
- 7) Occurrence of severe treatment adverse events (grade 3 or 4) based on common terminology criteria for adverse events (CTCAE), or death from any cause
- 8) Blood DSG 1 and 3 levels [Baseline week 0, week 4, 12, 20, 24, 36, 48, 60, 72, 96, 120, 144, 168, 192]
- 9) Blood lymphocyte level (CBC) [Baseline week 0, week 4, 12, 24, 36, 48, 60, 72, 96, 120, 144, 168, 192]
- 10) Blood CD19/20 mean B cell counts percentage [Time Frame: Baseline, week 4, 12, 20, 24, 36, 48, 60, 72, 96, 120, 144, 168, 180, 192]
- 11) Number of rescue therapy given

Baseline investigations prior to commencing therapy

General investigations:

- CBC
- Renal panel
- Liver panel
- Fasting Glucose/HbA1c
- Urine microscopy
- Urine pregnancy test in women of childbearing age
- Serum immunoglobulins for IgA deficiency
- B cell (CD19/20) enumeration

- DSG 1, 3 ELISA

Infective screen:

- HepBs Ag, Anti-HBs Ab, anti-HepBc total antibodies
- Anti-HCV IgG
- Anti HIV 1 and 2 (if indicated)
- CXR
- Interferon-gamma release assays

Patients who have positive IGRA test results

As Tuberculosis (TB) is endemic in Southeast Asia, should Interferon-gamma release assays result be positive, the patient will be reviewed by infectious diseases specialist and need treatment of latent TB treatment prior to starting Rituximab. Patients will need to have completed at least 4 weeks of isoniazid or treatment with other TB medications, before commencement of the study.

Patients who are HepBs Ag positive, or HepBs Ag negative and anti-HepBc Ab – positive

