Viral hepatitis is a major healthcare burden especially in Hong Kong, which is considered to be part of an endemic region. The seroprevalence of anti-HepBc is estimated to be as high as 37.3%,¹¹ therefore the exclusion of HepBs Ag positive and HepBc Ab positive patients were amended in study protocol, and these patients will be included in the study.

Baseline HepB DNA levels will be done for patients who are HepBs Ag positive, and anti-hepBc Ab positive

Patients will be monitored for AST and ALT levels at least every 3 months, HepBsAg and HBV DNA tests repeated whenever clinically indicated

Patients who are HepBs Ag positive – will be started on entecavir 0.5mg daily, and will be referred to a gastroenterologist for further follow up.

Patients who are HepBs Ag negative, and HBc Ab positive, with detectable HepB DNA levels – will be started on entecavir 0.5mg daily, and will be referred to a gastroenterologist for further follow up.

Patients who are HepBs Ag negative, HBc Ab positive, with no detectable HepB DNA levels, will be started on entecavir 0.5mg daily, and will be continued on entecavir for at least 18 months after completion of last dose of rituximab.^{12,13}

Monitoring and definitions of disease outcome parameters:¹⁴

- **Control of disease activity:** Time at which new lesions cease to form and established lesions begin to heal.
- **End of consolidation phase:** Time at which no new lesions have developed for a minimum of 2 weeks and approximately 80% of lesions have healed
- **Complete remission:** The absence of new or established lesions
- **Complete remission off therapy:** The absence of new or established lesions while the patient is off all systemic therapy for at least two months.
- **Relapse/flare:** Appearance of ≥ 3 new lesions/month that do not heal spontaneously within 1 week, or by the extension of established lesions, in a patient who has achieved disease control

Steroid regimen and tapering:

Prednisolone tapering³

Severe Pemphigus (PDAI ≥ 45):⁹

- Prednisolone 1mg/kg/day for 1 month, then 0.75mg/kg/day for 1 month then 0.5mg/kg/day for 1 month, then 0.3mg/kg/day for 1 month then 0.2mg/kg/day for 1 month, then 0.1mg/kg/day for 1 month then off

Moderate pemphigus (PDAI ≥ 15):⁹

- Prednisolone 0.5mg/kg/day for 1 month, then 0.3mg/kg/day for 1 month then 0.2mg/kg/day for 1 month then off

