Steroid sparing agents such as azathioprine or MMF are reduced to half the dose once the patient is successfully recruited into the study and will be tapered and stopped upon commencement of the study.

Relapse/ failure to achieve complete remission

- Additional infusion of weekly rituximab 375mg/m² BSA weekly x 4 will be given at the time of relapse/ or if patient fails to achieve complete remission 2 months from last dose of rituximab. After initial induction phase for both arms, the time between subsequent doses of rituximab for treatment of relapse should be at least 2 months apart.

Rituximab infusion protocol:

Pre-medications

- Paracetamol 1000mg one hour before Rituximab infusion
- IV Piriton 30 minutes before Rituximab infusion
- Methylprednisolone 100mg IV or Hydrocortisone 100mg IV half hour before Rituximab infusion

Preparation:

- IV Rituximab is prediluted at a dose of 500mg in 500ml of 0.9% normal saline (i.e. 1:1 dilution, 1 mg/ml)
- Initial infusion rate starts at a rate of 50mg/hr (50ml/hr)
- If no hypersensitivity/anaphylaxis reaction occurs, increase infusion rate in 50mg/hr (50 ml/hr) increments every 30 minutes

- Maximum infusion rate is 400 mg/hr (400 ml/hr)
- Subsequent infusion: start at rate of 100mg/hr (100 ml/hr), increase 100mg/hr (100 ml/hr) increments every 30 minutes
- Monitor temperature, BP HR, respiratory rate and SpO2 every 30 minutes

Adverse effects

Infusion-related:

- Fever, chills/rigors
- Injection site pain
- Nausea and vomiting
- Asthenia, headache, myalgia, giddiness
- Rhinitis, throat irritation
- Pruritus, rash
- Risk of infections
 - ** Infections including urinary tract infections, pneumonia, pneumocystic pneumonia, herpes simplex, herpes zoster, cytomegalovirus infection. Lung and brain abscess. Severe hypogammaglobulinaemia, and high-dose immunosuppressants may be possible risk factors for systemic infections
- Neutropenia
- Pyelonephritis
- Haemolytic anaemia
- Toxic epidermal necrolysis
- Parkinsonism

Intravenous immunoglobulins (IVIG)

Treatment dosage: 2g/kg over 2-5 days

Infusion Protocol

0 min	: 50ml/hour
15 min	: 75ml/hour
30 min	: 100ml/hour
45 min	: 125ml/hour
60 min	: 150ml/hour
75 min & beyond	: 180ml/hour

For patients receiving IVIG for first time, wait 30mins before 1st increase. Infusion rate should be less than 0.27ml/kg/hour in the following groups of patients:

- Renal insufficiency
- Diabetes mellitus
- ≥ 65 years of age
- Sepsis
- Paraproteinaemia

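### The Kaplan-Meier estimate of relapse or flare is tied to an undefined infusion period that has no common end in the two arms and leaves out about 60% or more of the planned follow-up

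*Protocol*

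**What the plan says.** Under Outcome measures, the protocol sets the Kaplan-Meier target as the "likelihood of reaching the endpoint of relapses or flares within the drug infusing period". It gives no start or end week for that period. The next sentence compares the arms' time-to-event curves with a log-rank test and names no window.

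The end of scheduled infusions depends on which passage is read:

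- **Arm 1, text:** "A total of 12 doses of rituximab will be given in 55 weeks".
- **Arm 1, schedule table:** also 12 doses, but the last two fall at weeks 76 and 77.
- **Arm 2, table:** the last IVIG is at week 76, with no condition attached. The summary bullet agrees: "A total of 12 doses of rituximab will be given and 12 cycles of IVIG will be given".
- **Arm 2, earlier bullet:** "If a patient was clinically free of disease at end of 24 weeks, additional infusions of IVIG will be given" at weeks 30 to 76. Read literally, other patients have their last scheduled infusion at week 24.
- **Both arms, section on relapse or failure to remit:** further rituximab is given at relapse, or "if patient fails to achieve complete remission 2 months from last dose of rituximab".

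Visits are monthly for six months, "then followed up for every 3 months up to 4 years starting from baseline visit". In the list of secondary outcomes, time to flare (outcome 2) has no time frame, while outcome 3 is "Duration of complete remission, evaluated by the PDAI activity score [Baseline up to end of study". A flare can be counted only "in a patient who has achieved disease control".

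**The concern.** The protocol has chosen a window for its flare estimate, and the choice has two faults.

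First, the window has no common end. If it closes at different weeks in the two arms, the two reported likelihoods refer to different lengths of exposure. If the conditional IVIG bullet governs and patients are censored at their own last infusion, response at week 24 decides how long an Arm 2 patient is observed, while Arm 1's scheduled courses have no such rule. Censoring would then be related to prognosis. Two analysts with the same data could report different flare percentages and different contrasts between the arms.

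Second, on every reading of the schedule, first flares after scheduled infusions end fall outside the estimate. The protocol's case for the combination is long-lasting remission, and that shows after infusions stop.

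**Working it through.** **Schedule ends.** Arm 1 text: weeks 0–3, 24–27 and 52–55 give 12 doses ending at week 55, which reproduces the stated figure. Arm 1 table: weeks 0–3, 24–27, 52–53 and 76–77 also give 12 doses, ending at week 77. Arm 2: 12 rituximab doses by week 24, and 7 + 5 = 12 IVIG cycles by week 76. The gap between arms is 1 week (77 v 76), 21 weeks (55 v 76), or 31 to 53 weeks for an Arm 2 patient who stops at week 24.

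**Follow-up left out.** Share = (follow-up − last infusion week) / follow-up. Follow-up is 192 weeks (last listed assessment) or 208 weeks (4 years).

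| Window ends at week | of 192 | of 208 |
|---|---|---|
| 77 | 115/192 = 59.9% | 131/208 = 63.0% |
| 76 | 116/192 = 60.4% | 132/208 = 63.5% |
| 55 | 137/192 = 71.4% | 153/208 = 73.6% |
| 24 | 168/192 = 87.5% | 184/208 = 88.5% |

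**Visits.** Months 1–6 plus months 9, 12, …, 48 give 6 + 14 = 20. Month 18 (week 78) onward is 11 visits, all after week 77. Month 15 (week 65) onward is 12 visits, all after week 55.

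**Effect on the estimate.** The documents give no flare rates, so these are assumptions, identical in both arms: a proportion p = 0.6 disease-free at week 24, with flare hazard h1 = 0.003 per week if free and h2 = 0.012 if not.

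- Flare-free probability: S(t) = p·exp(−h1·t) + (1 − p)·exp(−h2·t).
- Risk = 1 − S(t): 28.5% at week 55, 36.2% at 76, 36.5% at 77, 62.3% at 192 and 64.6% at 208.
- If patients who are not free leave at week e, Kaplan-Meier at week 76 estimates 1 − S(e)·exp(−h1·(76 − e)).

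Cases, with no true difference between arms:

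- (a) Arm 1 to week 55, Arm 2 to week 76: 28.5% v 36.2%. Arm 2 looks worse.
- (b) 77 v 76 weeks: 36.5% v 36.2%. No material distortion.
- (c) Arm 2 patients who are not free leave at week 24: 1 − 0.858 × 0.856 = 26.6% instead of 36.2%. Arm 2 looks better. If retreatment keeps them in until about week 36: 1 − 0.798 × 0.887 = 29.2%.
- (d) As (c) with exit at week 24, but these patients never gain control and so cannot flare (h2 = 0): 18.0% instead of 12.2%. Arm 2 looks worse.

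Over p = 0.5 to 0.7, h1 = 0.002 to 0.003 and h2 = 0.006 to 0.012, the gap is 5 to 8 points in (a). In (c) it is 3 to 14 points with exit at week 24 and 2 to 10 with exit at week 36. Over the same range, 39% to 53% of first flares by weeks 192–208 fall after week 77.

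**Effect on the test.** In simulation under (c) with exit at week 24, the null hazard ratio is about 0.79 (Arm 1 to week 55) or 0.74 (to week 77), against 1.00 for a window common to the trial. With 10 per arm, false positives total 4.3% to 5.5%: 3.1% to 4.3% favouring Arm 2 and 1.2% favouring Arm 1.

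**The case against.** The strongest reply has four parts.

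1. Only one sentence carries the limit. Time to flare, number of flares and the log-rank sentence do not, and duration of remission runs to the end of the study, so late flares are still collected. This is true, and it limits the damage. But the only time-to-flare estimate described is the restricted one, and it may then cover a different period from the test beside it.
2. Unequal administrative censoring does not bias Kaplan-Meier at a common week, so case (a) compares two points on one curve. This is correct: at week 55 both arms read 28.5%. The 5 to 8 points arise if each arm's likelihood is read at the end of its own infusion period, a reading the sentence allows and does not rule out.
3. Informative censoring needs the conditional bullet to govern and each patient to be censored at their own last infusion. The infusion period could equally be a trial phase, and the two schedule tables end one week apart. This stands, so the bias in (c) and (d) is conditional. The documents do not say which passage governs.
4. A longer window does not solve the problem of patients who never gain control and so can never flare. This also stands and needs its own sensitivity analysis.

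None of this touches the follow-up lost. Retreatment starts at relapse or failure to remit, so it does not bring back the first late flare of a patient in sustained remission.

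**Conclusion.** The concern holds and should be fixed. Two parts rest on the documents alone: no reading of the schedule gives both arms the same end week, and the window leaves out at least 59.9% of scheduled follow-up. The bias figures rest on assumed rates and on how the window is read. They range from negligible (case b) to 14 points, and the direction can go either way. At 10 per arm the total false-positive rate stays near 5%, although under (c) the rejections lean towards Arm 2. The fault lies mainly in the reported flare percentages, not in the test.

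**What to change.** Replace the window with one rule: estimate and compare time from randomisation to first flare over the same full scheduled follow-up in both arms, censoring only at death, withdrawal or end of follow-up, and never at the end of infusions. State that the log-rank test and outcome 2 use this window. If an infusion-period figure is wanted, report it as supplementary, read at one common week in both arms. A sensitivity analysis that counts rescue for non-remission as an event would address patients who never gain control. The Arm 1 text and table, and the conditional and unconditional Arm 2 passages, must be reconciled.

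The cost is one sentence; the visits are already scheduled. Reported flare-free percentages will be lower, possibly substantially (in the illustration, flare risk is 36% at week 76 but 62% to 65% at weeks 192–208), and more loss to follow-up will have to be reported.

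### The primary outcome has no time point over 4 years of follow-up, patients rescued for non-remission can count as relapse-free remitters, and the rescue passages do not agree

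*Protocol*

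**What the plan says.** **Primary outcome.** The whole definition is "Percentage of participants who achieve relapse-free complete remission". No week, window or duration is attached.

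**Secondary Outcomes.** Numbers 3, 5, 6, 8, 9 and 10 have time frames. Number 5, for example, reads "Time to initial complete remission, evaluated by the PDAI activity score [Baseline up to end of study". Rescue appears only as a count, in number 11.

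**Admission and follow up.** "Patients will be followed up monthly for the first 6 months, then followed up for every 3 months up to 4 years", counted from baseline.

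**Outcome measures.** The Kaplan-Meier analysis concerns the "endpoint of relapses or flares within the drug infusing period".

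**Monitoring and definitions of disease outcome parameters.** Complete remission means that no lesions are present; there is no minimum duration and no condition on rescue. A relapse or flare needs new or extending lesions in a patient whose disease was previously under control.

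**Extra rituximab.**
- Arm 1: a further weekly course "can be given at time of relapse/or if patient fails to achieve complete remission 2 months from last dose of rituximab".
- Relapse/ failure to achieve complete remission: a further weekly course "will be given at the time of relapse/ or if patient fails to achieve complete remission 2 months from last dose of rituximab". No arm is named.
- Arm 2: the list gives relapse or flare as the only trigger and adds IVIG to the course.

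**Late Arm 2 infusions.** The text says: "If a patient was clinically free of disease at end of 24 weeks, additional infusions of IVIG will be given". The Arm 2 table lists the same infusions with no condition.

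**The concern.** A percentage achieving a state has no fixed value until the time of assessment is fixed. Treatment is open-label, so the choice among readings could be made by people who know the allocation and have seen how patients fared. The primary also depends on how patients are counted who first failed to remit, received extra rituximab and then cleared. The protocol never addresses them directly, and its definitions admit them as successes by default. Because the passages governing that extra treatment differ, the number of such patients in each arm may depend on which passage a site follows. At stake is whether the primary result has one meaning, and whether it describes the randomised regimen alone or the regimen plus rescue.

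**Working it through.** The protocol gives no calculation for the primary, so there is no figure to reproduce. The check is mainly a comparison of passages.

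**1. Time frames.** The secondary outcomes are numbered 2 to 11, which makes ten. Six have a time frame (3, 5, 6, 8, 9, 10) and four do not (2, 4, 7, 11). The protocol therefore does set time frames at this level, but not for the primary.

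**2. Readings left open.** Scheduled visits after baseline: 6 monthly + (48 − 6)/3 = 14 three-monthly = 20. The primary could mean remission at any of these, remission at one selected later, or remission with no relapse to the end of follow-up.

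**3. Can the infusing period supply the date?** It is attached to the relapse or flare analysis, not to the primary. Its end is also unclear:

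| Arm | Text | Table |
|---|---|---|
| 1 | 4 + 4 + 4 = 12 rituximab doses, ending at week 55 | 4 + 4 + 2 + 2 = 12 doses, ending at week 77 |
| 2 | IVIG at weeks 30 to 76 if disease-free at 24 weeks, yet a total of 12 IVIG cycles is also stated | 7 IVIG to week 24, then 5 more to week 76 = 12, no condition |

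**4. How far the reading can matter (illustration; rates assumed, not from the protocol).** Suppose 90% remit initially and relapse occurs at a constant rate λ per year from baseline. The percentage still relapse-free at week w is 90 × exp(−λw/52).

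| λ | Ever remitted | Week 52 | Week 76 | Week 208 |
|---|---|---|---|---|
| 0.1 | 90 | 81 | 78 | 60 |
| 0.2 | 90 | 74 | 67 | 40 |
| 0.4 | 90 | 60 | 50 | 18 |

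This concerns the level of the percentage. It says nothing about a difference between arms.

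**5. The rescued patient.** There are two routes to the same result. (i) The patient never gains control, so cannot relapse by definition, is given extra rituximab and clears. (ii) The patient gains control, never flares, does not clear fully, is given extra rituximab and clears. In both, lesions are absent and no relapse has occurred, so the primary is met as worded.

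**6. The rescue passages side by side.**

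| Section | Non-remission a trigger? | Force | Arms |
|---|---|---|---|
| Arm 1 | Yes | Optional | 1 |
| Relapse/ failure to achieve complete remission | Yes | Mandatory | None named |
| Arm 2 | Not mentioned | Mandatory, for relapse or flare | 2 |

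Optional against mandatory is an explicit clash. The Arm 2 difference is an omission.

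**7. Weight of one patient.** With about 10 per arm, 1/10 = 10 percentage points.

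**8. A workable week.** Planned infusions end by week 76 (Arm 2) or, at the latest, week 77 (Arm 1 table). The next listed weeks are 84 (outcome 6 only) and 96 (outcomes 6, 8, 9 and 10). Week 96 is therefore the first later week at which all four are measured.

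**The case against.** **The word relapse-free narrows the primary.** A patient who clears once and later flares is not plainly relapse-free, so remission without relapse to the end of follow-up is a natural reading. This stands: a reader might infer that remission at any one visit suffices, but the text does not establish that. Neither does it establish the longer reading, so the ambiguity remains.

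**Arm 2 may not lack rescue for non-remission.** A reader might infer that only Arm 1 has it, and hence a bias in a known direction. The documents do not support that. The general section names no arm, and its next sentence, beginning "After initial induction phase for both arms, the time between subsequent doses of rituximab", speaks of both. The Arm 2 list omits the trigger without excluding it. The optional/mandatory clash remains.

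**Arm 2 infusions need not stop at week 24 for patients not yet clear.** The conditional sentence suggests it, but the table and the stated total of 12 IVIG cycles carry no condition. This is a further inconsistency, not a settled end date.

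**Time eligible for rescue does not measure bias.** Take 2 months as 8.7 weeks and count from the most recent planned dose. Up to week 76, Arm 1 has 12.3 (weeks 11.7–24) + 16.3 (35.7–52) + 12.3 (63.7–76) = 40.9 eligible weeks by its text. By its table it has 12.3 + 16.3 + 14.3 (61.7–76) = 42.9. Under the general section Arm 2 has 76 − 32.7 = 43.3. These are nearly equal. Large gaps appear only if extreme readings are combined, so no such range is claimed as the effect on the primary.

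**A SAP may settle this, and the trial is called a pilot.** Detailed handling of rescued patients could sit in a SAP. But the time point belongs to the endpoint definition, which the protocol supplies for other outcomes, and a SAP cannot reconcile treatment instructions. The protocol also states a superiority hypothesis and a two-sided 0.05 threshold, so the pilot label does not remove the need for one defined primary.

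**Conclusion.** The point holds in this form and should be fixed. The primary outcome has no time point and nothing elsewhere in the protocol supplies one. The definitions count a patient rescued for non-remission who then clears as a relapse-free remitter, whether or not control came first. The rescue passages and the text and table schedules are inconsistent.

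The direction and size of any bias between arms cannot be determined. The only firm size is 10 percentage points per reclassified patient, assuming the planned 10 per arm is reached. The endpoint defect rests on the text alone and is certain. The Arm 2 rescue point is weaker, because it rests on an omission that the general section may fill.

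**What to change.** 1. State one fixed time point for the primary, the same in both arms and after all planned infusions. Define success as complete remission at that visit with no protocol-defined flare before it. Week 96 is one workable choice, not the only sound one.
2. Before any comparison by arm, state whether patients rescued for non-remission count as successes or failures. Report the other definition as a supportive analysis, and tabulate rescues by arm and by reason (flare or non-remission).
3. The sponsor must reconcile the rescue wording in the Arm 1, Arm 2 and Relapse/ failure to achieve complete remission sections, and the text and table schedules of both arms. No clinical rule is proposed here.

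**Cost.** Protocol wording, a PDAI score at the chosen week, a reason code for each rescue, and slightly more analysis. The primary percentage may be lower than an ever-achieved figure. If week 96 is used, the remaining 208 − 96 = 112 weeks of follow-up inform only the secondary outcomes. That is a real loss in a trial interested in lasting remission, and the sponsor should weigh it when choosing the week.
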